8.7.2 Method of Detecting AEs and SAEs

Care will be taken not to introduce bias when detecting AEs and/or SAEs. Open-ended and non-leading verbal questioning of the patient is the preferred method to inquire about AE occurrences.

8.7.3 Follow-up of AEs and SAEs

After the initial AE/SAE report, the Investigator is required to proactively follow each patient at subsequent visits/contacts. All SAEs, will be followed until resolution, stabilization, the event is otherwise explained, through the follow-up contact, or the patient is lost to follow-up (as defined in Section 7.4). Further information on follow-up of AEs and SAEs is given in Section 11.7.

8.7.4 Regulatory Reporting Requirements for SAEs

- Prompt notification by the Investigator to the Sponsor of an SAE is essential so that legal obligations and ethical responsibilities towards the safety of patients and the safety of a blinded study medication under clinical investigation are met.

- The Sponsor has a legal responsibility to notify both the local regulatory authority and other regulatory agencies about the safety of a blinded study medication under clinical investigation. The Sponsor will comply with country-specific regulatory requirements relating to safety reporting to the regulatory authority, Institutional Review Boards (IRB)/Independent Ethics Committees (IEC), and Investigators.
- Investigator safety reports must be prepared for suspected unexpected serious adverse reactions (SUSAR) according to local regulatory requirements and Sponsor policy and forwarded to Investigators, as necessary.
- An Investigator who receives an Investigator safety report describing an SAE or other specific safety information (e.g. summary or listing of SAEs) from the Sponsor will review and then file it along with the IB and will notify the IRB/IEC, if appropriate according to local requirements.

8.7.5 Pregnancy

- Details of all pregnancies in female patients will be collected after the start of blinded study medication and until 30 days after the last dose of blinded study medication.
- If a pregnancy is reported, the Investigator should inform the Sponsor within 24 hours of learning of the pregnancy and should follow the procedures outlined in Section 11.8.
- Abnormal pregnancy outcomes (eg spontaneous abortion, fetal death, stillbirth, congenital anomalies, ectopic pregnancy) are considered SAEs.

8.7.6 Adverse Events of Special Interest

Adverse events of special interest have not been identified for ensifentrine.

8.7.7 Disease-related Events and/or Disease-related Outcomes Not Qualifying as AEs or SAEs

COPD exacerbations are an expected disease-related outcome. COPD exacerbations will not be collected as an AE unless they meet the definition of an SAE. COPD exacerbations should be captured on the COPD exacerbation eCRF (See Section 11.6).

8.7.8 Medical Device Incidents (Including Malfunctions)

The PARI LC Sprint nebulizer and PARI Vios PRO Aerosol Delivery System, and PARI BOY compressor or equivalent are being provided for use in this study for administration of blinded study medication.

In order to fulfill regulatory reporting obligations worldwide, the Investigator is responsible for the detection and documentation of events meeting the definitions of incident or malfunction that occur during the study with such devices.

The definition of a medical device incident, examples of incidents, and instructions for documenting and reporting medical device incidents are provided in Section 11.10.

Medical Device incidents fulfilling the definition of an AE/SAE will also follow the processes outlined in Section 11.7.

8.7.8.1 Time Period for Detecting Medical Device Incidents

- Medical device incidents or malfunctions of the device that result in an incident will be detected, documented, and reported during all periods of the study in which the medical device is used.
- If the Investigator learns of any incident at any time after a patient has been discharged from the study, and such incident is considered reasonably related to a medical device provided for the study, the Investigator will promptly notify the Sponsor.
- The method of documenting Medical Device Incidents is provided in Section 11.10.

8.7.8.2 Follow-up of Medical Device Incidents

- All medical device incidents involving an AE will be followed and reported in the same manner as other AEs (see Section 11.7). This applies to all patients, including those who discontinue blinded study medication.
- The Investigator is responsible for ensuring that follow-up includes any supplemental investigations as indicated to elucidate the nature and/or causality of the incident.
- New or updated information will be recorded on the originally completed form with all changes signed and dated by the Investigator.

8.7.8.3 Prompt Reporting of Medical Device Incidents to Sponsor/Sponsor Representative

- Medical device incidents will be reported to the Sponsor/Sponsor's designee within 24 hours after the Investigator determines that the event meets the protocol definition of a medical device incident.
- The Medical Device Incident Report Form will be sent to the Sponsor/Sponsor's designee by the same method as used for SAE reporting (Section 11.7).
- Contacts for Medical Device Incident reporting are the same as SAE reporting and can be found in Section 11.2 on the Medical Monitor Contact Information Page.

8.7.8.4 Regulatory Reporting Requirements for Medical Device Incidents

- The Investigator will promptly report all incidents occurring with any medical device provided for use in the study in order for the Sponsor/Representative to fulfill the legal responsibility to notify appropriate regulatory authorities and other entities about certain safety information relating to medical devices being used in clinical studies.

- The Investigator, or responsible person according to local requirements (eg, the head of the medical institution), will comply with the applicable local regulatory requirements relating to the reporting of incidents to the IRB/IEC.

8.7.9 COVID-19 Positive for Active Disease

An AE/SAE of positive COVID-19 active disease should be documented as any AE/SAE occurring in this study would be documented per the guidance throughout this section (Section 8.7). In addition, local guidelines for reporting COVID-19 to local and/or health authorities should be followed.

8.8 Treatment of Overdose

An overdose is defined as a dose greater than the total daily doses prescribed in this study which results in clinical signs and symptoms. These should be recorded by the investigator on the AE/SAE pages.

In the event of an overdose the investigator should use clinical judgement in treating the overdose and contact the study Medical Monitor. Verona Pharma is not recommending specific treatment guidance for overdose and toxicity management.

9.0 STATISTICAL CONSIDERATIONS

9.1 Statistical Hypotheses

The aim of this study is to show superiority of ensifentrine over placebo regarding selected efficacy measures. The null hypothesis to be tested for each endpoint will be that there is no difference between ensifentrine and placebo, against the alternative hypothesis that ensifentrine is better than placebo. All tests will be two-sided at a 5% significance level. Primary and key secondary endpoints used for claims will be tested in a sequential order to preserve the alpha level. Testing will stop once a not significant result is achieved. Test order will be FEV₁ AUC_{0-12h} at 12 weeks, peak FEV₁ at 12 weeks, weekly mean E-RS total symptom score at week 24, SGRQ total score at Week 24, morning trough FEV₁ at Week 12, FEV₁ AUC_{0-4h} at 12 weeks and proportion of SGRQ responders at 24 weeks.

9.2 Sample Size Determination

Approximately 800 patients will be randomized. The standard deviation for the change in FEV₁ AUC_{0-12h} is estimated to be 250 mL. With a 2-sided test at a 5% significance level and 500 vs. 300 evaluable patients in the two groups, there will be an 90% power to detect a true difference of 59 mL between the treatments. If the withdrawal rate at 24 weeks exceeds 25% overall, additional patients may be randomized to the study to compensate for the loss of data.

9.3 Populations for Analyses

mITT population: will include all patients randomized and treated with blinded study medication in the study. Patients will be handled as randomized in the mITT analyses.

PP population: will include all patients in the mITT without any major/important protocol deviations considered to have an impact on efficacy assessments. Reasons for exclusion will be specified at a Blind Data Review Meeting prior to database lock (DBL) and may include violations of inclusion/exclusion criteria, violations of withdrawal criteria, incorrect randomization, use of prohibited medication and non-compliance.

Safety set: will include all patients randomized and treated in the study. Patients will be handled by actual treatment in the safety analyses.

Pharmacokinetic set: will include all patients randomized to ensifentrine, receive at least one dose of ensifentrine, and have at least one quantified ensifentrine concentration at a scheduled PK time point after the start of dosing without important protocol violations and/or events with potential to affect PK concentrations.

The population PK analysis set will be defined in the modeling analysis plan.

9.4 Statistical Analyses

9.4.1 Efficacy Analyses

Efficacy analysis will primarily be performed on the mITT population. The primary endpoint and key secondary endpoints will also be evaluated using the PP population as a sensitivity analysis. Impact of imputations and various baseline characteristics will also be checked.

The primary endpoint, change from baseline in FEV₁ AUC_{0-12h} at Week 12, will be compared between treatments using an analysis of covariance (ANCOVA) model adjusting for treatment, region, background medication strata, and smoking status as factors and baseline FEV₁ as covariate. The estimated treatment difference with 95% confidence interval and associated (two-sided) p-value will be presented. Missing data will be imputed to get as close to the mITT population as possible. Primarily imputation will be based on data collected at visits performed after treatment withdrawal or at early termination visits even if outside visit window. When no such data is available, imputation will primarily be done using multiple imputation based on baseline characteristics and secondarily, as a sensitivity analysis, by the average change in the opposite treatment group as randomized to as a worst-case scenario. Further details on the handling of missing data will be given in the Statistical Analysis Plan.

Key secondary endpoints, FEV₁ AUC_{0-4h}, peak FEV₁, morning trough FEV₁, SGRQ total score and weekly mean E-RS total score, and other continuous secondary or exploratory endpoints will be assessed repeatedly during the study and the change from baseline to pre-specified time point of evaluation will be compared by similar ANCOVA models adjusting for treatment, region, background medication strata and smoking status as factors and baseline as covariate. Data collected at visits performed after treatment withdrawal or at early termination visits will be used in the analyses. Remaining missing data will primarily be imputed using multiple imputation based on baseline characteristics and data collected at post-randomization visits. Since assessed repeatedly, in contrast to primary endpoint, these data will also be analyzed for sensitivity by mixed model repeated measures models with treatment, visit and treatment by visit interaction as factors, baseline as covariate, subject as random factor and covariance structure by visit.

The proportion of responders on the SGRQ, patients with an improvement of at least 4 units, will be compared between treatment groups using a logistic regression model with fixed factors treatment, region, and background medication strata, and smoking status. Imputation of missing data will be done similar as for continuous endpoints. A sensitivity analysis will be performed in which patients with missing data at the required visit will be considered non-responder in the analysis.

The time to first COPD exacerbation during the 24 or 48 week treatment period, depending on stratification, will be visualized using a Kaplan-Meier plot and compared between treatment groups using the log-rank test, stratified by region, background medication strata, and smoking status. As a secondary evaluation a Cox's proportional

hazards model will be used with the same factors. Patients without exacerbations will be censored at last day in the treatment period, including period of recording after possible treatment withdrawal. The treatment difference in the Cox model will be expressed as a hazard ratio. Assumption of proportional hazards will be checked. The number of COPD exacerbations during the 24- or 48-week treatment period will be compared between treatments using a negative binomial model adjusting for treatment, region, background medication strata and smoking status and further using the log exposure time as an offset. The treatment difference from the negative binomial model will be expressed as an annualized risk ratio.

Subgroup analyses will be performed for the primary endpoint and selected secondary endpoints by gender, age-class (below or above 65 years), region, background medication strata, smoking status, ICS use, known chronic bronchitis, and FEV₁ reversibility at baseline ($\geq 12\%$ and ≥ 200 mL).

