| Efficacy Assessments and Associated Procedures | V0 | | V1 | V2 | V3 | V4 | V5 | | | | |
| Patient Contact Day Prior to Spirometry Visits ⁸ | | | X | X | X | | X | | | | X |
| COPD Exacerbation Assessment | | | X | X | X | X | X | X | | | X |
| Spirometry Training ⁹ | X | | X | X | X | | X | | | | |
| Spirometry (pre-dose) ¹⁰ | | | X | X | X | | X | | | | |
| Spirometry 0-4 hours post dose ¹⁰ | | | X | X | | | X | | | | |
| Spirometry 0-12 hours post dose ¹⁰ | | | | | X | | | | | | X |
| Health Outcomes ¹¹ | | | | | | | | | | | |
| SGRQ | | | X | X | X | | X | | | | |
| EQ-5D-5L | | | X | | X | | | | | | |
| BDI | | | X | | | | | | | | |
| TDI | | | | X | X | | X | | | | |
| Healthcare Utilization Assessment | X | | X | X | X | X | X | X | X | X | X |
| Patient Perception Survey | | | | | | | | | | | X |

Table 3: Schedule of Activities

| Study Assessments and Procedures | Screening 1 day Clinic Visit ¹ | Run-in Period 28 Days ± 4 Days Run-in | Procedures for Patients Completing 24-Weeks of Treatment | | | | | | | Procedures for Early Term/Withdrawal | | | |
|---|---|--|--|------------------------------------|-------------------------------------|-----------------------|-------------------------------------|--------------------------------------|------------------------------------|--------------------------------------|--|----------|--|
| | | | Day 1 (Rand) Clinic Visit ¹ | Week 6 Clinic Visit ^{1,2} | Week 12 Clinic Visit ^{1,2} | Week 18 Phone Contact | Week 24 Clinic Visit ^{1,2} | Follow up Phone Contact ³ | Early Term/Withdrawal ⁴ | Follow up Phone Contact ³ | | | |
| Issue eDiary to Patients Eligible to Enter Run-in | X | | V1 | V2 | V3 | V4 | V5 | | | | | | |
| Assess eDiary and E-RS Compliance (E-RS/EXACT-PRO will be on eDiary) ¹² | | | X | X | X | X | X | X | | | | X | |
| Collect eDiary | | | | | | | | X | | | | X | |
| Safety Assessments | | | | | | | | | | | | | |
| Vital Signs ¹³ | X | | X | X | X | | | X | | | | X | |
| 12-Lead ECG (pre-dose) ¹⁴ | X | | X | X | X | | | X | | | | X | |
| 12-Lead ECG (1.5 hours post dose) ¹⁴ | | | X | X | X | | | X | | | | X | |
| Physical Examination | X | | | | | | | | | | | | |
| AE Assessment | | | X | X | X | X | X | X | | | | X | |
| Laboratory Assessments | | | | | | | | | | | | | |
| Laboratory Tests Haematology, Chemistry (non-fasting), Pregnancy Test (serum) ¹⁵ | X | | X | | | | | X | | | | X | |
| Urine Pregnancy Test for Women ¹⁵ | | | X | X | | | | | | | | | |

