7.2.1 Reduced Assessments

The patient continues to follow the SoA (Section 1.3) and completes only the following assessments:

- Spirometry
- SGRQ
- COPD exacerbation
- AE
- Concomitant medication

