7.3.1 Early Termination/Withdrawal Procedures

If a patient is withdrawn prior to the Week 12 visit, every attempt should be made to have the patient complete the early termination/ withdrawal procedures in the SoA (Section 1.3) as soon as possible.

- If possible, patients should remain on blinded study medication and their maintenance LAMA or LABA medication and ICS (if applicable), follow the withholding procedures prior to Spirometry in Section 8.3.1.2, and should refrain from smoking or caffeinated beverages as recommended in Section 5.4.1.1.
- Patients unable to remain on blinded study medication and/or their maintenance LAMA or LABA medications and ICS (if applicable) should still complete the early termination/ withdrawal visit as soon as possible.

7.3.1.1 12-Hour Spirometry and 1.5 Hour ECG Procedures

For patients who are withdrawn prior to completing the Week 12 visit only, every attempt should be made to have the patient complete the 12-hour spirometry procedures and the ECG procedures at the early termination/withdrawal visit unless consent is withdrawn or the patient is being withdrawn for safety reasons precluding this assessment.

Patients who Continued Blinded Study Medication

Patients who have continued administration of their blinded study medication should complete the spirometry and ECG procedures as follows:

- Spirometry: Pre-dose and 0-12-hour post-dose assessments as per Section 1.4 and Section 8.3.1.
- ECG: Pre-dose and 1.5-hour post-dose ECG procedures as per Section 8.4.2.

Patients who Discontinued Blinded Study Medication

Patients who have discontinued blinded study medication prior to the early termination/withdrawal visit may optionally complete spirometry and ECG assessments at the early termination visit if they have not already completed the Week 12 assessments. These patients will not be dosed with blinded study medication. If possible, patients should start spirometry between 6 am and 10am, withhold rescue medication and/or maintenance LAMA or LABA medications for the time period specified in Section 6.7.2, and refrain from caffeinated beverages and/or smoking for the time period specified in Section 5.4.1. The spirometry and ECG procedures should be completed as follows:

- Spirometry: Serial spirometry at 0-hour, 30 min, and 1, 2, 4, 6, 8, and 12 hours.
- ECG: 12-lead ECG at 0-hour and 1.5 hours.

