9.4.4 Missing Data

All data collected after treatment withdrawal will be used in the analyses. Patients withdrawn from study will perform an End-of-Study visit after decision to withdraw the patient has been made. Data collected at such visits will be used for analysis even if outside the visit window for the endpoint. Remaining missing data will primarily be imputed using multiple imputation based on baseline characteristics and data collected at post-randomization visits. In addition, a worst-case scenario using the average change in the opposite treatment group will be used for imputation as a sensitivity analysis. For the responder analysis of SGRQ, patients with no available data for imputation will be considered non-responders as a sensitivity analysis. In exacerbation analyses, patients are included with data collected up to last day in the treatment period/period of recording following treatment withdrawal.

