6.4. WINDOWING CONVENTIONS

Each visit (except for Day 1 visit) will have a ± 10 days window. No visit windowing will be applied during the analysis to the data that is only collected at scheduled site visits for patients that have completed the study, and therefore the data will be presented as per the visit reported in the database.

For the patients that discontinued from the study, the End of Study (EOS) visit will be windowed to the corresponding visit, based on the study day, for questionnaire, spirometry and rescue medication data. The EOS visit can only be windowed to a visit that is missing or has a missing result. The rules for the windowing are described below.

- For spirometry raw data and derived data that happens at every visit, windowing will be done as per the corresponding visits.

- Day 1 = Day 1
 - Week 6 = after Day 1 and up to and including Day 53
 - Week 12 = after Day 53 and up to and including Day 95
 - Week 24 = after Day 95 and up to and including Day 179
- For spirometry derived data that only happen at certain visits, windowing will be done for the corresponding visits.
 - For morning trough:
 - Week 6 = after Day 1 and up to and including Day 53
 - Week 12 = after Day 53 and up to and including Day 95
 - Week 24 = after Day 95 and up to and including Day 179
 - For evening trough and AUC_{0-12h}:
 - Week 12 = after Day 1 and up to and including Day 95
- For rescue medication data, E-RS/EXACT-PRO, e-diary data and COPD exacerbation, windowing will be done as per the corresponding visits.
 - For patients who completed the study or who discontinued study medication but continue in the study:
 - Week 1 = Actual study Day of Week 24 visit minus 168 days (inclusive) up to and including actual study day of week 24 visit minus 161 days
 - Week 2 = Actual study Day of Week 24 visit minus 161 days up to and including actual study day of week 24 visit minus 154 days
 - Week 3 = Actual study Day of Week 24 visit minus 154 days up to and including actual study day of week 24 visit minus 147 days
 - Week 4 = Actual study Day of Week 24 visit minus 147 days up to and including actual study day of week 24 visit minus 140 days
 - Week 5 = Actual study Day of Week 24 visit minus 140 days up to and including actual study day of week 24 visit minus 133 days
 - Week 6 = Actual study Day of Week 24 visit minus 133 days up to and including actual study day of week 24 visit minus 126 days

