7.2. MULTICENTER STUDIES

This study will be conducted by multiple investigators at multiple centers internationally. Randomization to treatment arms is not stratified by country/ center.

When specified, statistical analysis will be adjusted for geographic region. Geographic region will be categorized as shown in Table 3:.

Table 3: Geographic Regions

Geographic Region	Country
Europe	Belgium, Bulgaria, Denmark, Hungary, Poland, Slovakia, Estonia, Spain
North America	United States, Canada

7.3.MISSING DATA

Missing safety data will not be imputed.

All data collected during the scheduled visits for patients on-treatment and off-treatment, for patients with treatment withdrawal, as well as the end-of-study visits for patients withdrawing from the study will be used for analysis performed on the mITT and that the remaining missing values will be handled as described in sections 16.1.2, 16.2.2 and 16.3.2 of the SAP.

7.4.MULTIPLE COMPARISONS/ MULTIPLICITY

To address multiplicity in the analysis of the endpoints, statistical testing of the primary endpoint and key secondary endpoints will be done in the hierarchical order (listed below). Initially the primary endpoint will be checked to see if comparison between active treatment and placebo is statistically significant. If yes, the first key secondary endpoint will be evaluated. If yes, the next key secondary endpoint will be evaluated. This process will continue until either all endpoints are evaluated, or if one of the endpoints' comparison is not significant.

Order of the endpoints that will be used for the hierarchical testing:

1. Change from baseline FEV₁ to FEV₁ AUC_{0-12h} at Week 12
2. Change from baseline FEV₁ to peak FEV₁ at Week 12
3. Change from baseline (i.e. mean over the last 7 days of run-in) to the mean weekly value at Week 24 in COPD symptoms, as measured by daily diary (E-RSTM:COPD)
4. Change from baseline in the SGRQ total score at Week 24
5. Change from baseline FEV₁ to morning trough FEV₁ at Week 12
6. Change from baseline FEV₁ to average FEV₁ AUC_{0-4h} at Week 12
7. Proportion of SGRQ responders at Week 24

7.5.EXAMINATION OF SUBGROUPS

Subgroup analyses will be conducted as stated in the efficacy analysis and disposition sections. Primary aim for the subgroup analysis is to check whether there are differences in treatment effect between strata or subgroups, which will be tested through interaction. For each analysis

by subgroup the results will be summarized as follows:

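### The Schedule of Activities shows no SGRQ (or TDI) at the Early Term/Withdrawal visit, although the protocol and SAP say data from that visit will be used

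*Protocol*

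**What the plan says.** **What the analysis expects.** Protocol 9.4.1 names SGRQ total score among the key secondary endpoints and states in the same paragraph: "Data collected at visits performed after treatment withdrawal or at early termination visits will be used in the analyses". Protocol 9.4.4 says of the exit visit of withdrawn patients: "Data collected at such visits will be used for analysis even if outside the visit window for the endpoint". SAP 6.4 maps the end-of-study visit of study discontinuers to a scheduled visit, "based on the study day, for questionnaire, spirometry and rescue medication data". SAP 7.3 uses scheduled visits on and off treatment, "as well as the end-of-study visits for patients withdrawing from the study will be used for analysis performed on the mITT".

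**What is collected at exit.** Table 3 marks SGRQ at Day 1 and Weeks 6, 12 and 24, and TDI at Weeks 6, 12 and 24. Neither row has an entry to the right of Week 24. For patients withdrawn before Week 12, Protocol 7.3.1 says that "every attempt should be made to have the patient complete the early termination/ withdrawal procedures in the SoA". Protocol 4.1 and 7.3 are the general text for all withdrawals: 4.1 requests the early termination procedures, and 7.3 points to the same schedule. The subsections of 7.3.1 give detail on spirometry and ECG only.

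**Patients who stop treatment but stay in the study.** Protocol 7.1 asks most of them to complete the withdrawal assessments and asks sites to retain them. Those who cannot keep to the full visits have three options. Under 7.2.1, "The patient continues to follow the SoA (Section 1.3) and completes only the following assessments", and SGRQ is on the list. Under 7.2.2, SGRQ is taken at Week 24. Under 7.2.3 (phone contact only) there is no SGRQ. TDI is on none of the three lists.

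**The concern.** A site that follows Table 3 collects no SGRQ at the visit from which the analysis text expects to draw data. SGRQ total score and SGRQ responders at Week 24 are positions 4 and 7 in the test order (SAP 7.4). They are also the only variables in the health-related quality-of-life estimand, which follows a treatment-policy strategy (SAP 2.5). For patients with no exit value, that estimand rests on a missing-at-random model instead of an observation.

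The reason for leaving may be related to outcome. Protocol 7.1.7 lists lack of efficacy among possible reasons for stopping study medication, and 11.6.7 ends study treatment after a second or a severe exacerbation.

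Two supports are also weaker for SGRQ than they look. The average-imputation analysis (SAP 16.1.2, extended to key secondary endpoints in 16.2.2.4) can use early-termination data, and for SGRQ none is scheduled. SAP 3.3 also drops the analysis that would have counted missing SGRQ as non-response.

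**Working it through.** No stated figure is in dispute, so the check is mainly of text against text.

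**1. The table rows.** SGRQ has four marks and TDI three, exactly their scheduled visits. Other rows of the same table, such as 0-12 hour spirometry and the COPD exacerbation assessment, do carry a mark in the last (Early Term) position.

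**2. Is the blank cell decisive?** Not by itself. The pre-dose spirometry row has the same pattern as SGRQ, yet Protocol 1.4 (Table 4) and 7.3.1.1 require pre-dose spirometry at early termination. The question is therefore whether other text adds the questionnaire in the same way. Sections 4.1, 7.3, 7.3.1 and 8.3.3 do not.

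**3. What SAP 6.4 can act on.** SAP 16.2.1.2 classes E-RS, SGRQ and BDI/TDI as questionnaires. SAP 6.4 gives day limits for spirometry (Days 53, 95 and 179) and weekly limits for rescue use, E-RS/EXACT-PRO, e-diary and exacerbation data. It gives none for SGRQ or TDI, so even an SGRQ collected at exit would have no explicit window.

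**4. What a withdrawal contributes.** A patient leaving at Week 20 has SGRQ at baseline, Week 6 and Week 12. Week 24 is imputed by the model in SAP 16.2.2.1, which uses treatment, region, the two strata, baseline and all scheduled visits. A patient leaving before Week 6 has baseline only. The responder outcome is recalculated from the imputed score (SAP 16.2.2.2).

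**5. Scale.** The withdrawal rates below are assumptions. The 25% comes from Protocol 9.2, where exceeding it may lead to randomizing more patients. The number is rate × arm size, with equal rates in both arms.

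| Study withdrawal | Of 800 | Ensifentrine (500) | Placebo (300) |
|---|---|---|---|
| 5% | 40 | 25 | 15 |
| 10% | 80 | 50 | 30 |
| 25% | 200 | 125 | 75 |

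Patients who stay in the study by phone only would come on top; the documents give no basis for their number.

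**6. Precision.** The plan's only power statement concerns FEV₁ AUC0-12h. With SD 250 mL, 500 vs 300 patients and a 59 mL difference, the standard error is 250 × √(1/500 + 1/300) = 18.26 mL. Then 59/18.26 − 1.96 = 1.27, a power of 0.898, which agrees with the stated 90%. This does not carry over to SGRQ, for which no SD or effect size is given. As an outer limit, if imputation recovered nothing, the SGRQ standard error would rise by 1/√(1 − d): 1/√0.95 = 1.03 at 5% and 1/√0.75 = 1.15 at 25%. Week 6 and 12 values in the model reduce this loss.

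**The case against.** The best case against has four parts.

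- **The table is unreliable on this point.** The text copy read here is imperfectly aligned. The Patient Perception Survey mark sits in the last position although Protocol 8.3.3.5 places it at Follow-up, and required pre-dose spirometry is blank at early termination. This stands as a reason to check the PDF. It does not remove the point, because pre-dose spirometry is required elsewhere and SGRQ and TDI are not.
- **The 9.4.1 sentence is generic.** It covers FEV₁, SGRQ and E-RS together, and says that data collected will be used, not that every instrument is collected. For SGRQ it already has content through 7.2.1 and 7.2.2. This is fair and makes the conflict softer. SAP 6.4, however, names questionnaire data at the end-of-study visit specifically.
- **Sensitivity analyses exist.** Opposite-arm average imputation and a tipping-point analysis are planned for key secondary endpoints (SAP 16.2.2.4). This stands, although SAP 16.2.4 introduces its list as performed at Week 12, so their use for Week 24 SGRQ should be confirmed. They test the assumption and do not supply the missing observation.
- **An exit SGRQ might change little.** Protocol 7.3.1 asks patients to stay on study medication through the exit visit where possible, so the value would often be on-drug. Patients lost to follow-up or withdrawing consent may attend no such visit. Both statements stand.

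A reader might infer that the SAP rule for end-of-study questionnaire data has nothing to act on. That goes too far, because it applies to E-RS, a daily diary measure. Nor can it be said that everyone leaving after Day 95 would have had an observed Week 24 value, since that limit is given for spirometry.

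**Conclusion.** The point holds as a mismatch between collection and analysis, subject to confirming the blank cells in the PDF. Study withdrawals, and treatment discontinuers who choose phone contact only, give no exit SGRQ. Their Week 24 SGRQ and responder status rest on missing-at-random imputation in the main analysis. Discontinuers under 7.2.1 and 7.2.2 are not affected for SGRQ.

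The number affected is not stated. The range of 40 to 200 of 800 assumes 5% to 25% study withdrawal. It is an upper bound on the study withdrawals an exit questionnaire could recover, and its top end is a trigger, not a forecast.

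A reader might infer that earlier visits are mostly better than the missing ones, so that the result is biased towards ensifentrine. The documents give nothing on the direction or size of any bias. TDI has the same gap but matters less: it measures dyspnea, lies outside the test hierarchy and is not in the quality-of-life estimand.

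**What to change.** Confirm the SGRQ and TDI cells of Table 3 in the source PDF. If they are blank:

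- Add SGRQ to the Early Term/Withdrawal column, completed before spirometry in the order of Protocol 8.3.3. Add TDI with lower priority.
- State in SAP 6.4 the day limits for mapping end-of-study SGRQ and TDI to Weeks 6, 12 and 24.

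The cost is one short questionnaire and one brief interview at a visit that already takes place, plus a few lines in the SAP. If collection can no longer be changed, Protocol 9.4.1 and 9.4.4 and SAP 6.4 and 7.3 should say that no early-termination SGRQ or TDI data are collected, so that the reliance on imputation is explicit.
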